10.3 End of Treatment/Visit 2 (Day 6)

With the exception of the CFRSD-CRISS administration and the blood and sputum samples for gallium and iron levels, the other Visit 2 procedures can be performed in any order in relation to the stop of the study drug infusion.

- 1. If not already completed for the day, administer CFRSD-CRISS.
- 2. Review subject diary.
- 3. Collect and review CFRSD-CRISS from days 2-6.
- 4. Record any AEs.
- 5. Record changes to concomitant medications.
- 6. Record weight.
- 7. Perform abbreviated physical examination.
- 8. Perform and record vital signs.
- 9. Perform and record oximetry.
- 10. Perform and record spirometry.
- 11. Assess infusion of study drug and stop infusion.
- 12. If applicable, remove the midline catheter, PICC, or peripheral IV.

Version 2.0 Version Date: 28 AUG 14 Page 34 of 57

- 13. Collect urine for urinalysis.
- 14. Collect blood for laboratory tests (hematology and serum chemistry) and, within 10 minutes of the stop of the infusion, for gallium and iron levels.
- 15. Collect expectorated sputum for gallium and iron levels within 10 minutes of the stop of the infusion.
- 16. Collect returned study drug supplies and perform accountability
- 17. Instruct the subject to drink two liters of fluid per day through Day 8.
- 18. Dispense subject diary and remind subject to complete the diary through Day 8.
- 19. Schedule subject for Visit 3.

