9.3 Pharmacokinetic Measurements

Because of limited correlation between clinical efficacy and PK measurements done in the previous Phase 1b study in CF, only limited PK assessments will be made. Expectorated sputum and blood (plasma) for determination of concentrations of gallium and iron will be collected predose and post-dose as detailed in the Table below:

PK Collection Day	Blood	Sputum
Day 1	 Pre-dose 	1 hr (+/- 10 minutes)
	• 1hr (+/- 10	post infusion start
	minutes) post	
	infusion start	

Version 2.0 Version Date: 28 AUG 14 Page 30 of 57

PK Collection Day	Blood	Sputum
Day 6	Prior to infusion stop	Prior to infusion stop
	(+/- 10 minutes)	(+/-10 minutes)
Day 14	At visit	At visit
Day 28	At visit	At visit
Day 56	At visit	At visit

The blood will be processed for plasma as detailed in the Study Laboratory Manual. All specimens will be labeled and placed immediately into a -70°C freezer. All frozen specimens will be shipped at the specified time frames, as detailed in the Study Laboratory Manual, throughout the study to a central laboratory.

Gallium and iron concentrations will be measured using inductively coupled plasma mass spectrometry (ICP-MS) done at a central laboratory.

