15.4 Analysis of Secondary Endpoints

Summary statistics (mean, standard deviation, median and range) of lung function parameters, sputum density, CFRSD-CRISS, and blood inflammatory markers for each visit and changes from baseline will be presented by treatment group. Descriptive statistics will be used to summarize the proportion of subjects initiating acute antibiotics (by route) and differences in proportions between the study arms will be estimated with accompanying 95% CIs.

Changes in lung function parameters (FVC in liters, FVC % predicted and FEV₁ % predicted), sputum bacterial density, CFRSD-CRISS, and inflammatory markers will be analyzed using MMRM. Adjusted means and 95% CIs will be presented for each visit. Treatment comparisons of the average response at each visit will be generated within the MMRM model based on the linear contrast of the average using the estimated LSMeans at Days 14, 28, and 56.

A log transformation will be used in all analyses of quantitative sputum culture counts and blood inflammatory markers. Change in bacterial density will include only those subjects with the pathogen at baseline. Additional descriptive analyses will be performed to summarize the disappearance and emergence of the pathogens and their susceptibility to gallium.

Version 2.0 Version Date: 28 AUG 14 Page 41 of 57

For those subjects randomized to receive IV gallium, we will determine of the Css and $t_{1/2\beta}$ by analyzing Days 1, 6, 14, 28 and 56. Clearance will be determined as the ratio of the infusion rate to the steady state concentration immediately prior to completion of the infusion. The $t_{1/2\beta}$ will be determined as 0.693/K where K is the elimination rate constant determined by the slope of the concentration/time curve after the infusion has been discontinued. To avoid unblinding, samples will only be assayed at the end of the completion of the trial.

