Serum Chemistry and Hematology Performed at Site Lab	x			
Blood Collection for Gallium and Iron Levels		X ^f	Χ ^f	
Blood Collection for Cytokines and Chemokines		Х		
Pregnancy Test (urine or serum)	х	х		
Urine Collection for Urinalysis at Performed Site Lab	х			

Version 2.0 Version Date: 28 AUG 14 Page 55 of 57

Task/Procedure	Visit 1 ^a (-1 to -6 days)	Visit 1 Day 1		Visits 2 – Visits 5 & Early Discontinuation of Study Drug
	Screening	Pre-Dose Baseline	Post- Dose	Refer to Combined Screening/Baseline Schedule of Events
Collect Expectorated Sputum for Microbiology		X ^g		
Collect Expectorated Sputum for PK			Xa	
Randomize subject		Х		
Obtain Venous Access		Х		
Study drug administration ^K			START	
Six-Hour Observation			Х	
Dispense Subject Diary ^m			Х	

^a Screening may occur on the morning of Day 1 prior to start of study drug. In this case, Screening, Baseline and Start of Treatment (Day 1) occur on the same day. Alternatively, Screening and Baseline/Day 1 may be separated into two visits as long as Screening takes place within 7 days of Baseline/Day 1.

Version 2.0 Version Date: 28 AUG 14 Page 56 of 57

^b Visit 2 should be scheduled at approximately the same time as Visit 1 as the study drug should be stopped at approximately the same time of day as it was started.

^c Subjects who withdraw from the study should be encouraged to come in for final visit procedures as described in section 12.2.

^d Subjects who discontinue the study drug early, should be encouraged to come in for the Early Discontinuation of Study Drug Visit (Section 10.6) and then proceed with all the remaining study visits. At Visit 2, perform all study procedures except for stopping the study drug administration, dispensing the subject diary, and collecting/counting returned study drug supplies (as these procedures will be performed as part of the Early Discontinuation of Study Drug Visit).

^e The CFRSD-CRISS diary will be completed daily from Day 1 through Day 6 and then again at Visits 3, 4, and 5.

f Day 1 blood for gallium and iron levels: pre-dose, and 1 hour (+/- 10 minutes) after initiating study drug infusion and Day 1 expectorated sputum for gallium and iron levels: 1 hour (+/- 10 minutes) after initiating study drug infusion.

^g Day 6 blood and sputum for gallium levels: prior to infusion stop (+/- 10 minutes)

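### The protocol gives conflicting times for the Day 6 gallium sample, before or after the infusion stops, so Css and clearance do not rest on one defined level

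*Protocol*

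**What the plan says.** - **Section 15.4** defines clearance as infusion rate divided by the "steady state concentration immediately prior to completion of the infusion". Section 5.2 lists Css and the elimination half-life as secondary endpoints; clearance is not listed.
- **Section 9.3** gives the Day 6 time for blood and for sputum as "Prior to infusion stop", followed by a tolerance of plus or minus 10 minutes. **Appendix 1, footnote g** repeats this: "Day 6 blood and sputum for gallium levels: prior to infusion stop (+/- 10 minutes".
- **Section 10.3** opens by saying that, apart from the symptom diary and the gallium and iron samples, "the other Visit 2 procedures can be performed in any order in relation to the stop of the study drug infusion". It does not say on which side of the stop the samples belong. Its list then runs: item 11, "Assess infusion of study drug and stop infusion"; item 12, "If applicable, remove the midline catheter, PICC, or peripheral IV"; item 14, blood "within 10 minutes of the stop of the infusion, for gallium and iron levels"; item 15, sputum with the same tolerance.
- **Section 9.2** allows blood to be taken through the study-drug access only when drug is not running. While it is running, another access point must be used.
- **Timing records.** Infusion stop times go into the subject diary, through Day 6 by footnote m but only through Day 5 by section 9.1.9. The protocol asks for a sample collection time only in section 10.7 and footnote h, when the infusion ended before an early-discontinuation visit.

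**The concern.** The analysis needs a level taken while the infusion is still running. The tolerance in section 9.3 and footnote g undoes the words it follows, since the plus side falls after the stop. The checklist that site staff will follow, read in order, puts the draw after the stop. Section 9.2 pushes the same way, because waiting until the drug is off can save a venepuncture.

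No other sample can stand in. During the infusion, gallium is sampled at 1 hour on Day 1 and again on Day 6, and section 1.2 reports steady state only by 48 hours. If sites read the instructions differently, the Css summary mixes on-infusion and off-infusion levels, and the protocol does not require the Visit 2 draw time that would tell them apart.

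**Working it through.** **1. Does the end-of-infusion level drive clearance?** Using the 61-hour levels in Table 1 of section 1.2, with clearance = rate / level:

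- 200 mg/m²/day: 200/24 = 8.33 mg/h/m²; 8.33/2.2 = 3.79 L/h/m². As a mean of individual ratios under a lognormal level: 3.79 × (1 + (0.6/2.2)²) = 4.07. Table 1 states 4.0.
- 100 mg/m²/day: 4.17/2.1 = 1.98; × (1 + (0.6/2.1)²) = 2.15. Table 1 states 2.1.

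The stated figures reproduce closely, so an error in the level passes straight into clearance.

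**2. Fall in 10 minutes for a single phase.** Fall = 1 − 2^(−(1/6)/h), h in hours.

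- Initial half-life, non-CF patients (section 1.2): 20.6% at 0.5 h, 10.9% at 1.0 h, 6.2% at 1.8 h.
- Terminal half-life: 0.46% at 25.1 h (non-CF mean), 0.09% at 129 h (CF, 200 mg/m²/day).

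**3. Share s of the end-of-infusion level in the fast phase.** The protocol does not give s, so it is an assumption. Two crude routes use Table 1 and take the AUC to run to infinity.

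- Flat level for 120 h, then terminal decline: s = 1 − (AUC − 120C)·(ln 2/h)/C. At 100 mg/m²/day: 1 − (503 − 252)/318 = 0.21. At 200 mg/m²/day: 1 − (537 − 264)/409 = 0.33.
- Two phases with the slow one still accumulating: plateau P = AUC/120; slow fraction F = (1 − C/P)/2^(−61/h); s = (1 − F)/[(1 − F) + F(1 − 2^(−120/h))]. This gives 0.38 and 0.47.

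If the AUC in the first route ended near Day 14, s would be about zero; near Day 28, about 0.19 and 0.29.

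**4. Fall at the last permitted minute.** Fall = 1 − [s·2^(−(1/6)/h) + (1 − s)·2^(−(1/6)/129)].

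| s | h = 0.5 h | h = 1.0 h | h = 1.8 h |
|---|---|---|---|
| 0.21 | 4.4% | 2.4% | 1.4% |
| 0.33 | 6.9% | 3.7% | 2.1% |
| 0.47 | 9.7% | 5.2% | 3.0% |

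Clearance rises by the reciprocal: a 3.7% fall gives +3.8%, a 9.7% fall gives +10.8%.

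**5. Average over the window.** Mean fast-phase loss for draws spread evenly over 0–10 minutes after the stop is 1 − (1 − e^(−x))/x, with x = (ln 2/h)/6. At h = 1.0 h this is 5.6%.

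- All draws after the stop: 5.6% × s = 1.2% (s = 0.21), 1.8% (0.33), 2.6% (0.47).
- Draws spread evenly on both sides: half of that, 0.6%, 0.9% and 1.3%.

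Over h = 0.5 to 1.8 h and these shares, the all-after average runs from 0.7% to 5.0%.

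**6. Yardstick.** The between-subject CV at 61 h is 0.6/2.2 = 27%. The standard error of a mean in 60 subjects is 27%/√60 = 3.5%.

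**7. Opposite direction.** Body surface is about 7.2/4.0 = 1.8 m², so a daily one-litre bag holds about 200 × 1.8 = 360 mg, or 360 µg/mL. Carry-over of 0.05 × 2.2/360 = 0.03% of the sample volume would cancel a 5% fall.

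**The case against.** A reader might infer that the protocol makes sites sample late, with the catheter already out, and so biases Css downward. The documents do not support that.

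- Section 9.3 and footnote g do say before the stop, and the tolerance in section 10.3 also admits a draw before it. The fault is a contradiction with a loose window, not a uniform late-sampling rule.
- Catheter removal is conditional, and the opening of section 10.3 leaves its order free.
- The sign is not assured, given sampling through the line under section 9.2.
- The fast-phase share depends on an AUC range that section 1.2 does not state, and the initial half-life comes from non-CF cancer patients. On the CF terminal phase alone the loss is 0.09%.

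All of this stands, and it limits the claim about size and direction. It is also fair that section 9.3 calls these limited PK assessments, that Css is determined in the gallium arm only, and that the sentence in section 15.4 defines clearance, which is not itself an endpoint. The Study Laboratory Manual, not shown, may ask for the draw time.

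None of this removes the conflict between the sections, and Css still depends on this one sample.

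**Conclusion.** The contradiction holds as a matter of text and needs no pharmacokinetic assumption: sections 9.3, 10.3 and footnote g do not agree with one another or with section 15.4.

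The consequence is minor. For clean venous draws after the stop, Css would read low by about 1–2% on average, and by up to roughly 7–10% for the latest draw at the shortest initial half-life and the larger assumed shares. The 20.6% figure is an outer limit that needs the whole level to fall at the fastest initial rate. The average is below the 3.5% standard error and far below the 27% between-subject spread. With carry-over from the line, the error could go the other way. Only secondary pharmacokinetic quantities are affected; the primary endpoint, alpha and sample size do not depend on this sample. It is worth correcting because the error is avoidable at small cost.

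**What to change.** Reconcile section 9.3, section 10.3 and footnote g to one rule that matches section 15.4:

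- Take the Day 6 blood and sputum in the 10 minutes before the pump is stopped, with no tolerance beyond the stop.
- Draw the blood from an access point other than the infusion line, as section 9.2 already requires while drug is running.
- List both samples ahead of item 11 in section 10.3.
- Make the matching change in section 10.7 and footnote h for infusions stopped at the visit.
- Record the sample clock time next to the stop time kept in the diary, and align section 9.1.9 with footnote m on the last diary day for infusion times.
- Flag samples drawn after the stop and show Css with and without them as a sensitivity summary. Automatic exclusion would discard data to avoid an error of about 1–2%.

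Cost: reordered steps, one time field and no extra sample. The real downside is a separate venous access for this draw in subjects who would otherwise be sampled through the line once the drug is off.

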10.4 Visit 3 (Day 14 +/-2 days)

- 1. Administer CFRSD-CRISS.
- 2. Review subject diary.
- 3. Record any AEs.
- 4. Record changes to concomitant medications.
- 5. Record weight.
- 6. Perform abbreviated physical examination.
- 7. Perform and record vital signs.
- 8. Perform and record oximetry.
- 9. Perform and record spirometry.
- 10. Collect blood for clinical laboratory tests (hematology and serum chemistries) and for gallium and iron levels.
- 11. Collect urine for urinalysis.
- 12. Collect expectorated sputum for gallium and iron levels.
- 13. Schedule subject for Visit 4

10.5 Visit 4 (Day 28 +/- 3 days)

- 1. Administer CFRSD-CRISS.
- 2. Record any AEs.
- 3. Record changes to concomitant medications.
- Record weight.
- 5. Perform complete physical examination.
- 6. Perform and record vital signs.
- 7. Perform and record oximetry.
- 8. Perform and record spirometry.
- 9. Collect blood for clinical laboratory tests (hematology and serum chemistries), gallium and iron levels, and cytokine and chemokine testing.
- 10. Collect urine for urinalysis.
- 11. Collect blood or urine for pregnancy test (if female of child-bearing potential).
- 12. Collect expectorated sputum for culture and gallium and iron levels.

Version 2.0 Version Date: 28 AUG 14 Page 35 of 57

13. Schedule subject for Visit 5.

10.6 Visit 5 (Day 56 +/- 4 days) - Final Visit

- 1. Administer CFRSD-CRISS.
- 2. Record any AEs.
- 3. Record changes to concomitant medications.
- 4. Record weight.
- 5. Perform complete physical examination.
- 6. Perform and record vital signs.
- 7. Perform and record oximetry.
- 8. Perform and record spirometry.
- 9. Collect blood or urine for pregnancy test (if female of child-bearing potential).
- 10. Collect blood for gallium and iron levels, and cytokine and chemokine testing.
- 11. Collect expectorated sputum for culture and gallium and iron levels.

10.7 Early Discontinuation of Study Drug

With the exception of the CFRSD-CRISS administration and the blood and sputum samples for gallium and iron levels, the other procedures can be performed in any order in relation to the stop of the study drug infusion (if subject did not already stop infusion prior to visit).

- 1. If not already completed for the day, administer CFRSD-CRISS.
- 2. Review subject diary.
- 3. Collect and review CFRSD-CRISS.
- 4. Record any AEs.
- 5. Record changes to concomitant medications.
- 6. Record weight.
- 7. Perform abbreviated physical examination.
- 8. Perform and record vital signs.
- 9. Perform and record oximetry.
- 10. Perform and record spirometry.
- 11. Assess infusion of study drug and stop infusion (if applicable).
- 12. If applicable, remove the midline catheter, PICC, or peripheral IV.
- 13. Collect urine for urinalysis.
- 14. Collect blood for laboratory tests (hematology and serum chemistry) for gallium and iron levels (If infusion stopped at visit, collect within 10 minutes of the stop of the infusion. If infusion stopped prior to the visit, note the collection time).
- 15. Collect expectorated sputum for gallium and iron levels (If infusion stopped at visit, collect within 10 minutes of the stop of the infusion. If infusion stopped prior to the visit, note the collection time).
- 16. Collect returned study drug supplies and perform accountability.
- 17. Instruct the subject to drink two liters of fluid per day for 2 more days.

Version 2.0 Version Date: 28 AUG 14 Page 36 of 57

- 18. Dispense subject diary and remind subject to complete the diary for 2 more days.
- 19. Schedule subject for Visit 2 and proceed with the remaining study visits. At Visit 2, conduct all procedures except for 10,11,15,16, and 17.

11 ADVERSE EXPERIENCE REPORTING AND DOCUMENTATION

11.1 Adverse Events

An AE is any untoward medical occurrence in a clinical investigation of a patient administered a pharmaceutical product and that does not necessarily have a causal relationship with the treatment. An AE is therefore any unfavorable and unintended sign (including an abnormal laboratory finding), symptom or disease temporally associated with the administration of an investigational product, whether or not related to that investigational product. An unexpected AE is one of a type not identified in nature, severity, or frequency in the current Investigator's Brochure or of greater severity or frequency than expected based on the information in the Investigator's Brochure.

The Investigator will probe, via discussion with the subject, for the occurrence of AEs during each subject visit and record the information in the site's source documents. AEs will be recorded in the patient CRF. AEs will be described by duration (start and stop dates), severity, outcome, treatment, serious criteria, and relation to study medication.

The investigator must continue to follow up on the AEs related to study drug until resolution or stability.

AE Severity

The National Cancer Institute's Common Terminology Criteria for Adverse Events (CTCAE) Version 4.03, as modified for CF, should be used to assess and grade AE severity, including laboratory abnormalities judged to be clinically significant. The modified criteria can be found in the study manual. If the AE is not covered in the modified criteria, the guidelines shown in Table 1 below should be used to grade severity. It should be pointed out that the term "severe" is a measure of intensity and that a severe AE is not necessarily serious.

Table 1. AE Severity Grading

Severity (Toxicity Grade)	Description
Mild (1)	Mild; asymptomatic or mild symptoms; clinical or diagnostic
	observations only; intervention not indicated
Moderate (2)	Moderate; minimal, local or noninvasive intervention indicated; limiting age-appropriate Instrumental activities of daily living (e.g.,
	preparing meals, using the telephone, managing money)
Severe (3)	Severe or medically significant but not immediately life-threatening; hospitalization or prolongation of hospitalization indicated; disabling; limiting self care activities of daily living (e.g., bathing, dressing, feeding self, using toilet, taking medications)
Life-threatening (4)	Life-threatening consequences; urgent intervention indicated
Death (5)	Death related to AE

Version 2.0 Version Date: 28 AUG 14 Page 37 of 57

AE Relationship to Study Drug

The relationship of an AE to the study drug should be assessed using the following the guidelines in Table 2.

Table 2. AE Relationship to Study Drug

Relationship to Drug	Comment
Definitely	Previously known toxicity of agent; or an event that follows a reasonable temporal sequence from administration of the drug; that follows a known or expected response pattern to the suspected drug; that is confirmed by stopping or reducing the dosage of the drug; and that is not explained by any other reasonable hypothesis.
Probably	An event that follows a reasonable temporal sequence from administration of the drug; that follows a known or expected response pattern to the suspected drug; that is confirmed by stopping or reducing the dosage of the drug; and that is unlikely to be explained by the known characteristics of the subject's clinical state or by other interventions.
Possibly	An event that follows a reasonable temporal sequence from administration of the drug; that follows a known or expected response pattern to that suspected drug; but that could readily have been produced by a number of other factors.
Unrelated	An event that can be determined with certainty to have no relationship to the study drug.

11.2 Serious Adverse Experiences (SAE)

An SAE is defined as any AE occurring at any dose that results in any of the following outcomes:

- death
- a life-threatening adverse experience
- inpatient hospitalization or prolongation of existing hospitalization
- a persistent or significant disability/incapacity
- a congenital anomaly/birth defect

Other important medical events may also be considered an SAE when, based on appropriate medical judgment, they jeopardize the subject or require intervention to prevent one of the outcomes listed.

11.2.1 Serious Adverse Experience Reporting

Study sites will document all SAEs that occur (whether or not related to study drug) on an SAE Report Form. The collection period for all SAEs will begin after informed consent is obtained and end after procedures for the final study visit have been completed.

All SAE Report Forms will be reviewed by the site investigator and sent to the TDNCC within one business day of the site learning of the event. Sites will scan and email or fax the SAE report to:

Version 2.0 Version Date: 28 AUG 14 Page 38 of 57

Protocol Number: GALLIUM-IP-13 Confidential

Email address: [contact]

Direct dial [contact]

The site will notify the TDNCC of additional information or follow-up to an initial SAE Report as soon as relevant information is available. Follow-up information is reported on an SAE Report Form.

SAEs will be reported to the DSMB in accordance with the Data Safety Monitoring Plan.

In accordance with the standard operating procedures and policies of the local Institutional Review Board (IRB), the site investigator will report SAEs to the IRB. The Sponsor will report SAEs to the FDA in accordance with 21 CFR 312.

